12.5. Missing Data

Missing data will be entered according to the following established coding scheme: (1) Not Applicable = 9999; (2) Refused = 7777; (3) Missing due to impaired vision = 8888; and (4) Reason for missing data unknown 5555.

12.6. Data back up

Data files are entered and stored on a secure, encrypted network maintained by Jefferson that is backed up twice daily.

13.1. Data Analyses

We will use descriptive statistics to characterize the sample, assess randomization success, and as a final data quality check. We will analyze survey metrics (e.g., treatment satisfaction with PREVENT and EUC) by summing responses across items and reporting means and SDs. For outcome analyses, we will use an intent-to-treat approach (i.e., all participants with any follow-up data are included as randomized). Any missing data are considered missing at random (MAR); we will apply models that yield valid estimates under this assumption. For analyses of continuous outcomes, we will check assumptions of normality and homoskedasticity of errors using checks of model residuals. We will transform outcomes as appropriate prior to analyses and will use SPSS, SAS, TreeAge Pro, and Mplus software as indicated.

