13.1.1. Secondary Aims

- 1. Test the efficacy of PREVENT to increase perceived access to care over 12 months (secondary outcome). Hypothesis: PREVENT will increase Patient Satisfaction Questionnaire-18 (PSQ-18) scores to a greater extent than EUC over 12 months.
- 2. Test the efficacy of PREVENT to increase realized access to care over 12 months (secondary

outcome). Hypothesis: PREVENT will increase the number of received Diabetes Quality Metrics to a greater extent than EUC over 12 months.

3. Test the efficacy of PREVENT to improve DM self-care over 12 months (secondary outcome). Hypothesis: PREVENT will improve Diabetes Self-Care Inventory (DSCI) scores to a greater extent than EUC over 12 months.

Analyses: For Secondary Aims 1 – 3, we will model PSQ-18 scores, number of received Diabetes Quality Metrics, and DSCI scores as continuous variables to estimate average change in each of these three variables over time by treatment group. We will use mixed effects linear regression with fixed effects for time (baseline, and months 6 and 12), randomization assignment, and time by randomization interaction. A random intercept term and an appropriate covariance structure will be used to account for correlation among repeated measurements. Within this model we will estimate the average change in PSQ-18 scores, number of received Diabetes Quality Metrics, and DSCI scores, respectively, by treatment group, from baseline to 6 months, from 6 to 12 months, and from baseline to 12 months. For each of these 3 Secondary Aims, the primary hypothesis will be tested by comparing the groups with respect to change from baseline to 12 months.

4. Determine if increasing subjective and/or objective indicators of access to care and/or DM self-care mediates PREVENT's reduction of DM-related ED visits and/or hospitalizations. Hypothesis: PREVENT will reduce DM-related ED visits and/or hospitalizations to the extent that it increases subjective and/or objective indicators of access to care and/or improves DM self-care.

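### Limiting the intent-to-treat set to participants with follow-up data can drop baseline-only participants whom the mixed models need for validity under MAR

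*Combined protocol and SAP*

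**What the plan says.** Section 13.1 (Data Analyses) explains its intent-to-treat approach as "all participants with any follow-up data are included as randomized". It continues: "Any missing data are considered missing at random (MAR); we will apply models that yield valid estimates under this assumption".

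For Secondary Aims 1 to 3, section 13.1.1 (Secondary Aims) specifies "mixed effects linear regression with fixed effects for time (baseline, and months 6 and 12), randomization assignment, and time by randomization interaction". Baseline is therefore a level of the response, not a covariate. On the correlation it says: "A random intercept term and an appropriate covariance structure will be used to account for correlation among repeated measurements". Changes are to be estimated "by treatment group, from baseline to 6 months, from 6 to 12 months, and from baseline to 12 months", and the hypothesis is tested by "comparing the groups with respect to change from baseline to 12 months". Section 13.1.3 carries the same approach over to HbA1c, health beliefs, depression and quality of life.

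Other parts bear on who has follow-up data:

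- Sections 6.2 and 6.7 provide for chart review of all randomized participants at 6 and 12 months.
- Section 6.4 keeps the 12-month attempt open for someone who missed month 6.
- Section 6.6 asks the assessor to gather what can be gathered by telephone when a visit is missed.
- Section 12.1 compares completers with those lost and adjusts for variables that differ significantly.

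The plan does not say whether follow-up data is judged per participant across all sources or separately for each outcome. It gives no expected dropout.

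**The concern.** A likelihood-based mixed model is valid under MAR because it uses all observed values, including those that predict who goes missing. With baseline as a response, a baseline-only participant is an incomplete record, and the observed baseline score is what corrects for loss related to baseline. An inclusion rule that requires follow-up removes that record before the model is fitted. What remains is a set selected on retention. If low scorers leave, those who stay have a high mean baseline, and their regression toward the mean is read as change over time.

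At stake are the estimated within-arm changes for the questionnaire outcomes and HbA1c and, if selection works differently in the two arms, the between-arm test. The label is also affected: a set conditioned on post-randomization data is a modified intent-to-treat set for any outcome to which the rule is applied in this way.

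**Working it through.** The plan states no figure to reproduce, so the check is of the logic, followed by its size under assumed inputs.

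**Inputs from the documents.** 78 participants randomized per arm (section 5.1); response times 0, 6 and 12 months; tested contrast is the difference in change from 0 to 12 months (section 13.1.1, Secondary Aims).

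**Assumed inputs, because the documents give none.** SD 1 at each visit; baseline to 12-month correlation ρ, equal in both arms; share d with no follow-up at all, equal in both arms; logistic loss depending on the observed baseline only, with slope b per SD (so the data are MAR).

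**Formula.** Among those retained, the mean 12-month score is the true mean plus ρ·m, where m = E[Y₀ | retained] with the baseline centred at 0. The expected change is therefore the true change plus ρ·m − m, so

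bias of an arm's mean change = (ρ − 1)·m, and bias of the contrast = (ρ − 1)·(m₁ − m₂).

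Here m = ∫ y(1 − p(y))φ(y)dy / (1 − d), where p is the logistic loss probability with its intercept set so that the average loss is d.

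**Loss related to baseline in one arm only, ρ = 0.5.** Low scorers leave that arm, and m = 0 in the other:

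| Lost (d) | m, b = −0.7 | m, b = −1.0 | Contrast bias = −0.5·m |
|---|---|---|---|
| 5% | 0.034 | 0.047 | −0.017 to −0.024 |
| 10% | 0.067 | 0.091 | −0.033 to −0.045 |
| 20% | 0.130 | 0.173 | −0.065 to −0.087 |

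If high scorers leave instead, or if it happens in the other arm, the sign reverses. With ρ from 0.3 to 0.7 and b = −1.0, the 20% figure runs from 0.7 × 0.173 = 0.121 to 0.3 × 0.173 = 0.052 in absolute size.

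**Other mechanisms.**

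- Missing completely at random (MCAR): m = 0 in both arms, so there is no bias.
- The same baseline-dependent mechanism in both arms: m₁ = m₂, so the contrast bias is 0. Each arm's own mean change is still off by (ρ − 1)·m, for example 0.087 SD at 20% lost and b = −1.0.

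**Simulation at the trial's size.** 78 per arm, true difference 0, ρ = 0.5, random-intercept likelihood with time by arm, 3,000 runs; one-arm loss, b = −1.0, d = 20%:

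| Analysis set | Bias of contrast (SD) | Type I error |
|---|---|---|
| Only those with follow-up | −0.093 | 0.082 |
| All randomized with a baseline value | −0.007 | 0.055 |

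With the same mechanism in both arms, the follow-up-only set gave a contrast bias of −0.001 to −0.002 and type I error of 0.050 to 0.055.

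**Scale.** At ρ = 0.5 the SD of change is √(2 × (1 − 0.5)) = 1. With about 62 retained per arm (0.8 × 78 = 62.4), the standard error of the contrast is √(2/62) ≈ 0.18. A bias of 0.087 is just under half of that.

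**The case against.** The strongest reply is that the rule is written per participant. Chart review is planned for every randomized participant, so someone with chart data but no interview has some follow-up data, stays in the set, and keeps the baseline questionnaire rows in the model. On that reading few people are lost and the problem nearly vanishes. This stands as a real possibility, but section 13.1 does not choose between the two readings, so the stated rule leaves the model's input open.

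Second, losing all follow-up is harder than it looks. The questionnaires can be taken by telephone, a missed month 6 does not close month 12, and only HbA1c needs a sample. A reader might infer that all these outcomes depend on a home visit, or that something like a fifth of participants would be excluded. The documents support neither.

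Third, a reader might infer that the rule biases the treatment comparison as such. It does not: the contrast is unaffected under MCAR or a mechanism common to both arms. EUC matches PREVENT in intensity (section 9.2) and the retention measures cover both arms (section 8.5). Against that, participants are not masked and only PREVENT has Behavioral Activation and telehealth, so arm-specific loss is plausible but not shown.

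Fourth, section 12.1 adjusts for baseline variables related to attrition. That helps in principle: in the scenarios simulated, using baseline as a covariate in the follow-up-only set left a bias of only −0.006 to 0.003 SD. But the rule depends on a significance test and does not say how a baseline score is to be controlled when it is also a response.

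**Conclusion.** The point holds in conditional form. Read outcome by outcome, the stated set discards observed baseline scores that the specified model needs, and the assurance "we will apply models that yield valid estimates under this assumption" no longer holds for PSQ-18, DSCI and the exploratory outcomes that share the model. The within-arm changes are biased if loss depends on baseline; the tested contrast is biased only if that dependence differs between arms, or if the baseline to 12-month relation does. Participants who miss just one of the two follow-up visits are still handled correctly.

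The size is modest. Under the one-arm assumptions above it is about 0.02 SD at 5% lost and 0.07 to 0.09 SD at 20%, and close to nothing if chart data keeps participants in the set. Loss rate, correlation and slope are all assumptions.

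Two outcomes fall outside the point. The primary count rests on chart review with a follow-up-time offset, and a participant with no time at risk adds no information to it. Diabetes Quality Metrics come from medical records, so they do not depend on the assessment visits.

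**What to change.** In section 13.1, replace the definition of the analysis set with: 'All randomized participants are analysed in the arm assigned. The mixed models include every randomized participant with at least one observed value of that outcome, including baseline only.'

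This settles the per-participant or per-outcome ambiguity and restores the stated MAR property. The baseline scores are already scheduled for collection before randomization, so the cost is a change of wording, with no statistical downside. Constraining the two arms to a common baseline mean is an optional change of model and is not needed to remove this bias.

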13.1.1. Primary Aim

Test the efficacy of PREVENT to reduce the number of incident DM-related ED visits and/or hospitalizations over 12 months (primary outcome). Hypothesis: PREVENT will halve the number of incident DM-related ED visits and/or hospitalizations relative to EUC over 12 months.

Primary Statistical Approach: The primary outcome measure is a count of DM-related ED visits and/or hospitalizations. We will use Poisson regression to model the number of outcome events as a function of randomization assignment, adjusting for the stratification variables and using follow-up time as the offset term. We will consider baseline variables (e.g., age, sex, education, cognitive functioning, insurance, polypharmacy (i.e., taking ≥ 5 medications), and medical comorbidity) as possible covariates if they relate to outcome events at the bivariate level with p<0.2. Negative binomial regression will be considered if there is evidence of over- or under-dispersion of the data.] From the model, we will calculate estimates of annual rates of the primary outcome and the adjusted estimate of the rate ratio. We will evaluate the primary hypothesis by testing the null hypothesis that the rate ratio for randomization assignment equals 1.

To examine the impact of treatment adherence on outcomes, we will calculate the Complier Average Causal Effect (CACE) and compare it to the intent-to-treat estimate. We will define adherent participants as those who: 1) receive ≥ 4 of 9 treatment sessions, and 2) have a telehealth visit with the PCP, and 3) achieve ≥ 2 DM self-care treatment goals. CACE will estimate treatment effects by comparing the outcomes in adherent PREVENT participants vs. EUC participants who would have been adherent had they been assigned to PREVENT. The adherence status for EUC participants, however, is not observable. Through the use of a latent class model, the CACE is estimable under certain assumptions. Part of the model includes using baseline covariates and adherence status in PREVENT participants to predict adherence status in EUC participants. This analysis will enable us to estimate the impact of adherence on study outcomes.

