PREVENT will begin soon after the participant's index ED visit, when many patients remain uncertain how to manage DM or how to access follow-up care. Community Health Workers (CHWs), who are race-concordant with participants, will: 1) deliver in-home DM education to increase participants' knowledge and skills; 2) use DM-specific Behavioral Activation to improve DM self-care; and 3) facilitate telehealth visits with the participant's primary care physician (PCP) and a DM nurse educator to increase access to care. The control treatment, EUC, is usual medical care that is enhanced with DM self-care education. EUC matches PREVENT in treatment intensity (i.e., 6 in-home sessions over 4 months, and 3 booster sessions over the next 8 months) and delivery of culturally relevant DM education, but does not include DM-specific Behavioral Activation or telehealth visits. The treatment comparison will identify PREVENT's specific efficacy over and above EUC.

This RCT is significant as the population ages and becomes more racially diverse, and as ED use and costs increase. This RCT is innovative because it: 1) tests the first ED-to-community intervention designed to reduce the need for ED care in AAs with DM; 2) assesses both subjective and objective indicators of access to care; and 3) defines the specific characteristics of PREVENT that confer its cultural relevance. If successful, PREVENT will meet Healthy People 2020's twin goals of reducing the personal and societal costs of DM and achieving health equity for all Americans.

The Specific Aims of this RCT are:

Primary Specific Aim: Test the efficacy of PREVENT to reduce the number of incident DM-related ED visits and/or hospitalizations over 12 months (primary outcome) in AAs with DM. Hypothesis: PREVENT will halve the number of incident DM-related ED visits and/or hospitalizations relative to EUC over 12 months.

The Secondary Aims are to:

- 1. Test the efficacy of PREVENT to increase perceived access to care over 12 months (secondary outcome). Hypothesis: PREVENT will increase Patient Satisfaction Questionnaire-18 scores to a greater extent than EUC over 12 months.
- 2. Test the efficacy of PREVENT to increase realized access to care over 12 months (secondary outcome). Hypothesis: PREVENT will increase the number of received Diabetes Quality Metrics (e.g., hemoglobin A1c testing, urine screening) to a greater extent than EUC over 12 months.

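### The gap between the CACE and the intent-to-treat estimate does not measure the impact of adherence, and it can suggest one when adherers and non-adherers benefit equally

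*Combined protocol and SAP*

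**What the plan says.** Section 13.1.1 (Primary Aim) adds a supplementary analysis of adherence to the Poisson model for the primary count: "we will calculate the Complier Average Causal Effect (CACE) and compare it to the intent-to-treat estimate". Adherence in the PREVENT arm needs all three of: "receive ≥ 4 of 9 treatment sessions", "have a telehealth visit with the PCP" and "achieve ≥ 2 DM self-care treatment goals". The CACE contrast is between adherent PREVENT participants and "EUC participants who would have been adherent had they been assigned to PREVENT". Adherence cannot be observed in EUC, so the plan relies on a model with baseline covariates: "Through the use of a latent class model, the CACE is estimable under certain assumptions". Those assumptions are not listed. The paragraph closes: "This analysis will enable us to estimate the impact of adherence on study outcomes". No interval, test or rule is given for the comparison. The efficacy conclusion rests on the ITT rate ratio being tested against 1.

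**The concern.** The stated question is what adherence does to outcomes. The stated method sets the effect in everyone randomised beside the effect in a subgroup defined by how they would behave if offered PREVENT. Neither quantity compares the same people at higher and lower adherence. If the model assumes that assignment does nothing for non-adherers, most of the gap is arithmetic: the whole ITT effect is attributed to the adherent share.

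At stake is the reading of the result. A CACE rate ratio further below 1 than the ITT ratio is likely to be reported as evidence that PREVENT works better when adhered to, and the closing sentence invites this. The same pattern appears when adherers and non-adherers benefit to the same degree.

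**Working it through.** **Inputs from the document.** 78 randomised per arm (section 5.1). Effect scale is a rate ratio with null value 1 (section 13.1.1). EUC "does not include DM-specific Behavioral Activation or telehealth visits" (Introduction), so non-adherence to PREVENT is one-sided. The document gives no adherent share, event rate or CACE figure, so there is nothing to reproduce.

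**Assumed inputs.** Adherent share p from 0.4 to 0.8; EUC rate 0.5 to 1.0 per year; untreated rate in would-be adherers either equal to that in non-adherers or 0.6 times it; Poisson counts without overdispersion. Simulations used 4,000 trials per scenario, with a binary baseline covariate predicting adherence and latent-class fits with and without the exclusion restriction.

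**Formulas.** Let a and b be the EUC rates in would-be adherers and non-adherers, RRc and RRn the PREVENT rate ratios in each, and w = p·a / (p·a + (1 − p)·b).

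- In general: RR_ITT = w·RRc + (1 − w)·RRn.
- Under the exclusion restriction RRn = 1: CACE rate difference = ITT rate difference / p, and RR_ITT = w·RRc + (1 − w).

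**Step 1: the arithmetic gap.** With the restriction and a = b, w = p and CACE RR = 1 − (1 − RR_ITT)/p. For an ITT ratio of 0.80:

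| p | CACE RR |
|---|---|
| 0.4 | 1 − 0.20/0.4 = 0.50 |
| 0.6 | 1 − 0.20/0.6 = 0.67 |
| 0.8 | 1 − 0.20/0.8 = 0.75 |

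**Step 2: on the ratio scale the share is not the only driver.** Take p = 0.6 and a CACE of 0.50. With a = b, RR_ITT = 0.6 × 0.5 + 0.4 = 0.70. With a = 0.6·b, w = 0.36/(0.36 + 0.40) = 0.474 and RR_ITT = 0.474 × 0.5 + 0.526 = 0.76. Same share and same CACE, but a different gap.

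**Step 3: equal benefit, RRc = RRn = 0.70, p = 0.6, rate 1 per year in both groups.** True CACE and true ITT are both 0.70. A simple moment calculation that imposes the restriction gives EUC non-adherers the rate seen in PREVENT non-adherers, 0.70. The EUC rate in would-be adherers is then (1.00 − 0.4 × 0.70)/0.6 = 1.20, and CACE = 0.70/1.20 = 0.58. The latent-class fit also uses the covariate and moves less: median 0.62 with the restriction, with CACE below ITT in about 85% of trials. Without the restriction the median was about 0.70, and CACE was further from 1 than ITT in 54% of trials, close to even.

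**Step 4: non-adherers benefit more (0.4 against 0.7), p = 0.6, a = 0.6·b.** True ITT = 0.474 × 0.7 + 0.526 × 0.4 = 0.54, so the true CACE of 0.70 is nearer to 1 than ITT. The restricted fit gave a median of 0.47, on the wrong side of ITT; the unrestricted fit gave 0.67.

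**Step 5: no effect in anyone.** Both true values are 1. The median latent-class CACE with the restriction was 0.98 to 1.01. It was further from 1 than ITT in 67–84% of trials (60–80% without the restriction), but further from 1 and favouring PREVENT in only 36–47%. The extra distance is noise: at p = 0.6 and rate 1.0 the SD of the log rate ratio was 0.16–0.17 for ITT and 0.26–0.31 for CACE.

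**Is Step 3 realistic here?** A participant with one to three sessions is non-adherent. By section 9.1, session 2 brings the PCP telehealth visit and session 3 the nurse telehealth visit and a Behavioral Activation action plan. Someone who stops after session 3 may therefore have received both components that separate PREVENT from EUC. A participant who attends all nine sessions but achieves one goal is also non-adherent, and goal achievement is a result of treatment rather than receipt of it. Assuming no effect in these people is doubtful.

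**The case against.** The strongest defence has four parts.

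- *CACE is correctly defined, and efficacy rests on ITT.* Both are true. The fault is confined to the purpose and interpretation given to the comparison.
- *Under the exclusion restriction, CACE is often taken as the effect of actually receiving treatment among those who would take it.* That reading applies to CACE itself, not to its distance from ITT. It also requires the whole effect of assignment to run through meeting the adherence threshold, which this definition makes hard to defend.
- *The plan does not say that it imposes the restriction.* This stands. Without it the gap has no fixed direction, as Step 4 shows. But the meaning of the gap then depends on an assumption left unstated. Even a well-estimated difference would compare two kinds of participant, not the same participants with and without adherence.
- *The plan sets no decision rule for the gap.* Also true, but the closing sentence supplies an interpretation without one.

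Two stronger readings are tempting and do not hold. A reader might infer that the comparison produces an apparent adherence benefit even when PREVENT does nothing. It does not do so systematically: with no effect both true values are 1, chance gaps have no systematic direction, and CACE is less precise. A reader might also infer that the gap is fixed by the adherent share alone. That is too strong on the plan's ratio scale, where the untreated rates also enter (Step 2).

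**Conclusion.** The point holds as an error of interpretation in a supplementary analysis. The CACE–ITT comparison cannot estimate the impact of adherence. If the exclusion restriction is imposed, it can point systematically to an adherence effect that does not exist: a median CACE of about 0.62 against an ITT of 0.70 when the true ratio is 0.70 in both groups. That size rests on an assumed 60% adherent share, 1 event per year, equal untreated rates and Poisson counts. Overdispersion would widen the noise without changing the direction of the findings. The primary ITT test is not affected. The change is worth making because it is cheap and prevents a false conclusion about adherence.

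**What to change.** Keep the CACE model and change what is reported and claimed.

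1. Delete the sentence "This analysis will enable us to estimate the impact of adherence on study outcomes" and the opening phrase that gives the impact of adherence as the purpose.
2. Add wording such as:

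> CACE estimates the PREVENT versus EUC rate ratio among participants who would adhere if assigned to PREVENT. It will be reported with its 95% CI and the observed adherent share. The exclusion restriction (no effect of assignment in non-adherers) and the covariates in the latent-class model will be stated, and the model will be fitted with and without that restriction. The difference between CACE and the ITT estimate will not be interpreted as an effect of adherence. The efficacy conclusion rests on the ITT test.

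The cost is a few sentences, one additional model fit and giving up a claim that the analysis cannot support. The unrestricted fit leans on how well baseline covariates predict adherence and on the assumed count distribution, so it serves as a sensitivity analysis rather than a replacement.
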